[figure not shown]
Study Protocol and Statistical Analysis Plan

The cluster randomized controlled trial will be conducted in Bangkok communities supported by Thaicare. A total number of 30,000 participants will be enrolled from 10 areas. (3,000 from each area). Participants from each area will be divided into three groups according to the accommodation type. The ratio between intervention group 1 to intervention group 2 and control group will be 1:1:1. The characteristics of population in each stratum will be reproduced as closely as possible. Cluster randomization by software will be used to blind the order of randomization. Demographic data (i.e., age, gender, weight, height, body mass index), concomitant diseases, income, type of accommodation, vaccination profile) of the control and intervention groups will be collected. The collection of data and the obtaining of the consent will be conducted by Socialgiver volunteers. There will be 2 intervention groups. Group 1 will receive 4 rapid antigen kits at the beginning of the study and will be asked to conduct a weekly self-test for 3 weeks. Group 2 will receive 7 rapid antigen kits at the beginning of the study and will be asked to conduct a twice-weekly self-test for 3 weeks (total of 6 tests). This is illustrated in Fig 1.

[figure not shown]

Fig 1. Self-tests schedule of each group.

Categorical variables will be presented in percent and frequency and analyzed by Chi square. Continuous variables will be presented in medians and interquartile range. Mixed effect logistic regression and incidence rate ratio will be used to model the difference in COVID-19 infection between the intervention and control groups, and between the two intervention groups. Statistically significant will be achieved at < 0.05 (P-values <0.05). Statistical Package for Social Sciences (SPSS) software (version 27, SPSS, Inc, Chicago, IL, USA) will be used.

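### Past COVID-19 infection is not among the listed baseline data, so chance imbalance in it between clusters can be neither described nor adjusted for: a modest loss of precision, not a bias

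*Combined protocol and SAP*

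**What the plan says.** The document is a single section with a design paragraph and an analysis paragraph.

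- **Baseline data.** The design paragraph gives a list. It opens with "Demographic data (i.e., age, gender, weight, height, body mass index" and ends with "concomitant diseases, income, type of accommodation, vaccination profile) of the control and intervention groups will be collected". Past COVID-19 infection, serology and a baseline infection test are not in the list, and nothing elsewhere supplies them.
- **Balance.** The plan states an aim, "The characteristics of population in each stratum will be reproduced as closely as possible", but names neither the characteristics nor the method.
- **Design.** "The cluster randomized controlled trial will be conducted in Bangkok communities supported by Thaicare". Enrolment is given as "A total number of 30,000 participants will be enrolled from 10 areas. (3,000 from each area"). Allocation is 1:1:1 across two intervention groups and a control group. Within each area, "Participants from each area will be divided into three groups according to the accommodation type"; whether these groups are strata or the randomised units is not clear. The number of randomised clusters is not stated.
- **Time frame.** Self-testing runs for three weeks. Group 1, for example, "will be asked to conduct a weekly self-test for 3 weeks".
- **Analysis.** Infection is to be modelled by mixed effect logistic regression and an incidence rate ratio. The random effects are not specified, and no adjustment covariate is named, not even vaccination.

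**The concern.** The outcome is COVID-19 infection over a short window. The plan records one source of immunity (vaccination) but not the other (earlier infection). A community that has recently had an outbreak may have fewer susceptible people for the next few weeks, whichever arm it falls in. Because whole clusters are randomised, a characteristic shared within clusters is balanced only as well as the number of clusters allows; 30,000 individuals do not settle the matter.

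If the item is not recorded at baseline, the trial cannot show whether the arms were alike on it, cannot use it to sharpen the estimate, and cannot answer a reader who asks. Asking later is a poor substitute, because recall could differ between arms that were testing and the arm that was not. The point concerns past, resolved infection, not infection already present at the first self-test.

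**Working it through.** **Inputs from the documents.** 10 areas x 3,000 = 30,000 participants; at 1:1:1, 30,000/3 = 10,000 per arm. The documents give no infection rate, prevalence of past infection, intracluster correlation or cluster count, so there is no stated figure to reproduce on this point.

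**Assumed inputs.** Mean prevalence of recent infection p = 0.20; between-cluster SD s = 0.10; protection over the window e = 0.5 to 0.8; k = 10 clusters per arm (one per arm per area).

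**Step 1: movement of the rate ratio by chance imbalance alone, with no effect of testing.**

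SD of log rate ratio = e x s x sqrt(2/k) / (1 - e x p)

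- e = 0.5: 0.5 x 0.10 x 0.447 / 0.90 = 0.025; exp(1.96 x 0.025) = 1.05
- e = 0.8: 0.8 x 0.10 x 0.447 / 0.84 = 0.043; exp(1.96 x 0.043) = 1.09

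With s = 0.15 the SDs are 0.037 and 0.064, and the factors 1.08 and 1.13. With s back at 0.10, 30 clusters per arm give 1.03 and 1.05, and 100 per arm give 1.02 and 1.03.

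The formula treats clusters as unmatched. If each area contains all three arms, area-wide differences in past infection cancel within area and these factors shrink.

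**Step 2: validity and precision.** Null trials were simulated (20,000 per scenario; two arms of about 10,000; assumed three-week risk 3%; clusters not matched by area; past infection measured without error). Type I error and the reduction in standard error (SE) were:

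| Clusters per arm | p, s, e | Clustering ignored | Analysed by cluster | By cluster, adjusted | SE reduction |
|---|---|---|---|---|---|
| 10 | 0.20, 0.10, 0.5 | 6.1% | 5.1% | 5.1% | 2% |
| 10 | 0.20, 0.10, 0.8 | 8.6% | 5.4% | 5.6% | 9% |
| 10 | 0.30, 0.15, 0.8 | 14.0% | 5.0% | 4.8% | 23% |
| 100 | 0.20, 0.10, 0.5 | 5.1% | 5.0% | 5.1% | 0% |
| 100 | 0.20, 0.10, 0.8 | 5.4% | 5.1% | 4.9% | 1% |
| 100 | 0.30, 0.15, 0.8 | 6.3% | 5.4% | 5.2% | 4% |

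**Step 3: cross-check of the precision gain.** With 300 expected infections per arm (10,000 x 0.03), sampling error alone gives an SE of log rate ratio of sqrt(2 x 0.97/300) = 0.080. Adding the Step 1 variance gives sqrt(0.080² + 0.025²) = 0.084 and sqrt(0.080² + 0.043²) = 0.091. Perfect adjustment could therefore remove at most about 4% to 12% of the SE. The simulated 2% and 9% are a little lower because the covariate's slope must be estimated from only 20 clusters.

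**Reading.** When clusters are respected, type I error is about 5% with or without the covariate. What the covariate buys is precision, and only a noticeable amount if clusters are few.

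**The case against.** A reader might infer that, without this item, differences in outbreak immunity cannot be told apart from the effect of self-testing, so that the comparison is biased. The documents do not support that. Chance differences between randomised clusters, measured or not, are random error. The plan specifies a mixed effect model, and with a random effect for the randomised cluster such variation enters the standard error. The inflation to 6-14% at 10 clusters per arm arises only if clustering is ignored. The plan does not name its random effects or say how the incidence rate ratio allows for clusters, but that is a separate gap, and a question on past infection would not close it.

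A reader might also picture a large gap between arms, such as 10% against 30% recently infected. Under the inputs above the SD of the difference between arms is 0.10 x sqrt(2/10) = 4.5 points, so a 20-point gap is about 4.5 SDs; even with a between-cluster SD of 15 points (6.7 points for the difference) it is about 3 SDs. Chance would almost never produce it, and it should not be used to size the problem.

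Other objections stand in part. Matching within area, if that is the design, would reduce the imbalance. Many clusters would make it negligible. Self-reported history misses undiagnosed infections, so the real gain would be below the simulated one. A randomised trial does not need every predictor of outcome measured to be valid. It could be said that past infection falls under concomitant diseases, but that term is undefined and would not ordinarily cover a resolved infection.

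What remains is that the omission is real, and that the plan's stated aim of reproducing population characteristics cannot be checked on an obvious one for this outcome.

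**Conclusion.** The point holds as a low-priority improvement. Past infection is not in the listed baseline data, so imbalance in it can be neither described nor adjusted for. The cost is precision, conditional balance and some credibility, not bias, on condition that the randomised cluster is fitted as a random effect.

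The best single indication of size is the 95% factor of about 1.05-1.09 on the incidence rate ratio at 10 clusters per arm, with an SE saving of about 2-9%. At 100 clusters per arm the saving is 0-4%, and the upper end of that needs 30% prevalence, an SD of 15 points and 80% protection. Every one of these figures rests on assumed prevalence, spread, protection, infection risk and cluster count. Confidence in the size is therefore low; confidence that the item is not listed is high.

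**What to change.** - Add one item to the baseline data the volunteers already collect, asked identically in all three arms before kits are given: whether the participant has ever had COVID-19 and, if so, the month of the most recent episode.
- Prespecify it as a covariate in the infection models (for example none, within the last 3 months, earlier), together with the vaccination profile and alongside a random effect for the randomised cluster. Collecting the item without naming it in the analysis would achieve little, since no covariate is named at present.
- Report the cluster-level proportion with past infection by arm.

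The cost is one question and one covariate, with no extra staff, tests or participants. The small downside is self-report error: undiagnosed infections are missed, which reduces the gain.

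### The plan names no small-sample reference distribution for the infection contrasts; if the randomised clusters number 30 or 10, an uncorrected Wald test at 0.05 would reject a true null too often

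*Combined protocol and SAP*

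**What the plan says.** The document is one unnumbered section. Its design paragraph opens: "The cluster randomized controlled trial will be conducted in Bangkok communities supported by Thaicare". It continues: "A total number of 30,000 participants will be enrolled from 10 areas", that is, "3,000 from each area". Within areas, "Participants from each area will be divided into three groups according to the accommodation type", and "The ratio between intervention group 1 to intervention group 2 and control group will be 1:1:1". On allocation it says only "Cluster randomization by software will be used to blind the order of randomization". That sentence does not say whether the cluster is an area, a group within an area, or a community, and the number of communities is not given.

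The analysis paragraph states: "Mixed effect logistic regression and incidence rate ratio will be used to model the difference in COVID-19 infection between the intervention and control groups". It adds a comparison of one self-testing arm with the other, which makes three pairwise contrasts. The criterion is "Statistically significant will be achieved at < 0.05 (P-values <0.05", and sidedness is not stated. SPSS version 27 is named without a procedure or options. The text gives no random effect, estimation method, degrees-of-freedom rule, intracluster correlation (ICC), expected infection risk or small-sample method.

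**The concern.** In a cluster trial, the precision of an arm contrast is limited by the number of randomised clusters, however many people each contains. A Wald z test, or a t test with degrees of freedom counted from 30,000 records, treats the between-cluster variance as known. With few clusters that variance is poorly estimated, and maximum likelihood also estimates it too low. Both faults remain after the correct random effect is in the model, so naming the random effect would not settle the matter.

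At stake are the P-values and confidence intervals for all three infection contrasts, on the odds ratio and on the incidence rate ratio. A chance difference between a few communities could be reported as an effect of self-testing.

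**Working it through.** **Inputs from the plan.** 10 areas, 3,000 people per area, three groups per area, three arms at 1:1:1, alpha 0.05 (two-sided assumed). The plan's own total reproduces: 10 × 3,000 = 30,000. It gives nothing from which power or a design effect could be computed.

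**Assumed inputs.** Infection risk 1-5%; ICC 0 to 0.05 on the latent logistic scale, where cluster variance = ICC/(1 − ICC) × π²/3 (0.033 at ICC 0.01, 0.173 at ICC 0.05).

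**Step 1: cluster counts the text allows.**
- Area-by-accommodation groups: 10 × 3 = 30 clusters of about 1,000, 10 per arm, which meets 1:1:1. Degrees of freedom: 30 − 3 = 27, or 30 − 3 − 9 = 18 with area as a block.
- Whole areas: 10 clusters of 3,000. These can only split 4/3/3 (12,000/9,000/9,000), so 1:1:1 cannot be met exactly. Degrees of freedom: 10 − 3 = 7.
- Communities: number not given; 100 is used as an illustration.

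**Step 2: analytic size of a nominal 5% Wald z test.** With an unbiased variance, size = P(|t_df| > 1.96). With a maximum-likelihood variance, which divides by the k clusters instead of by df, size = P(|t_df| > 1.96 × √(df/k)).

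| Clusters | df | Unbiased variance | Maximum-likelihood variance |
|---|---|---|---|
| 10 | 7 | 9.1% | 14.5% (cut-off 1.96√(7/10) = 1.640) |
| 30 | 27 | 6.0% | 7.4% (cut-off 1.96√(27/30) = 1.859) |
| 30, area as block | 18 | 6.6% | 14.6% if area effects are fixed (cut-off 1.96√(18/30) = 1.518) |
| 100 | 97 | 5.3% | 5.7% |

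**Step 3: simulated null trials.** Random-intercept logistic model, correctly specified, maximum likelihood by adaptive quadrature, Wald z. There were 800 trials per scenario, with a Monte Carlo standard error of about 0.8 points per contrast. Entries are means over the three contrasts, across risks of 1% and 5%.

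| Clusters | ICC 0 | ICC 0.001 | ICC 0.01 | ICC 0.05 |
|---|---|---|---|---|
| 10 | 4.2-4.8% | 5.6-8.2% | 10.4-13.3% | 14.7-14.8% |
| 30 | 3.9-4.7% | 3.9-5.0% | 6.0-8.7% | 7.7-7.9% |
| 100 | 4.1-5.0% | 4.7-5.2% | 5.2-5.7% | 5.0-5.1% |

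A second set (600 trials per scenario, risk 2-5%, cluster variance 0.1-0.3 on the logit scale) gave 14.2-15.4% for 10 clusters and 6.1-6.9% for 30.

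**Step 4: what restores the level.** In the second set, a cluster-level t test gave 5.4-5.8% (10 clusters) and 4.1-5.0% (30 clusters). Putting t critical values on the maximum-likelihood fit gave 5.1-6.0% with 30 clusters but still 8.7-9.8% with 10, so the variance estimate must be corrected as well.

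**Step 5: effect on interval width.** Ratio of t to z critical values: 2.052/1.960 = 1.05 (27 df), 2.101/1.960 = 1.07 (18 df), 2.365/1.960 = 1.21 (7 df).

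**The case against.** The strongest reply is that the plan commits to none of the things that produce the inflation. P<0.05 sets alpha; it does not choose a Wald z test, maximum likelihood or record-based degrees of freedom. A corrected analysis is left open, not ruled out. The cluster count and ICC are also unknown. This stands, and it rules out several readings that a reader might be tempted to make.

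- *The trial's false-positive rate is 6-15%.* The text does not support this as a fact. It joins two different designs, and with about 100 communities, or an ICC near 0, the rate is close to 5%.
- *14-15% is the likely figure.* It needs 10 whole areas as clusters, which cannot meet the stated ratio, or else 30 clusters with area effects fitted as fixed and a maximum-likelihood variance. The plan specifies neither of those choices.
- *All the P-values will be too small.* With 30 clusters and ICC 0.001 or less, simulated size was 3.9-5.0%.

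In the second set of simulations, the excess for 30 clusters is only 1-2 points. The Monte Carlo standard error there is √(0.05 × 0.95/600) = 0.9 points for one contrast and at best 0.5 pooled over three, so the lowest values are barely distinguishable from 5%. The analytic 6.0-6.6% carries no simulation error and points the same way.

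Two things limit the reply. First, the clustering needed is modest. At risk 2% and logit variance 0.1, the ICC on the proportion scale is about 0.02 × 0.98 × 0.1 = 0.002, yet with 3,000 people per cluster the design effect is 1 + 2,999 × 0.002 = 7.0. Second, a prespecified analysis should not leave open a choice that can move the error rate this far on the only unit counts the document gives.

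It is also fair to say that the undefined randomised unit is the prior gap, and that confounding would be the larger problem if arms coincided with accommodation type. That is a separate issue which no degrees-of-freedom method can repair.

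**Conclusion.** The point holds conditionally. The plan leaves the randomised unit, the cluster count and the reference distribution unstated. If a large-sample Wald test is used and between-cluster variation is not negligible (ICC about 0.01 or more), type I error per contrast is:

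- **30 clusters** (the reading that fits 1:1:1): about 6-7%, up to about 9% with a maximum-likelihood variance, and more only if area effects are also fitted as fixed under maximum likelihood.
- **10 clusters**: about 9-15%.
- **About 100 clusters**: close to 5%. An ICC near 0 gives the same at any of these counts.

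On the better-fitting reading the error is modest. It is still worth correcting before analysis, because the correction is standard and needs no new data. Confidence is medium, because the cluster count, ICC and infection risk are all assumed.

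**What to change.** State the randomised unit and the number of clusters per arm. Keep alpha at 0.05 and say that it is two-sided. Then add one prespecified method to the analysis paragraph, for example:

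*Each infection contrast (odds ratio and incidence rate ratio) will be estimated by restricted (pseudo-)likelihood with a random effect for the randomised cluster and tested with Satterthwaite degrees of freedom for that cluster. A supporting cluster-level analysis will follow the actual allocation, use a t reference on the between-cluster degrees of freedom, and apply a stated rule to clusters with zero infections.*

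The zero-infection rule is needed because a log risk is undefined for such clusters, and they become likely if clusters are many and small. The size of the restricted-likelihood test was not simulated here; that of the cluster-level t test was, which is why it is kept as support. The sponsor should confirm that the SPSS procedure chosen offers these options.

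The cost is one or two sentences and a few lines of code. Intervals widen on the log scale by about 5-7% with 30 clusters and about 21% with 10, and hardly change if clusters are many. If clustering proves negligible, a t reference is somewhat conservative: at ICC 0.001 or less, t critical values on the maximum-likelihood fit gave simulated sizes of 3.2-3.9% with 30 clusters and 1.3-3.4% with 10.
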